- Planned surgery including dental implants, tooth extractions, orthodontia are prohibited.
- Participation in any other clinical study during this study is prohibited.

If a prohibited therapy becomes a necessary treatment for the safety or best interest of the subject, the Sponsor Medical Expert should be notified, time permitting, to discuss possible alternatives prior to administration of a prohibited therapy.

If a subject receives prohibited therapy during the clinical study, the Sponsor should be notified to discuss the pertinence and the modalities for the subject to continue in the clinical study.

Effective

Version: 10.0

	Title 43USTT1904 CSP Infraorbital Hollows	Doc id MA-40833
---	---	---------------------------

Table 1: Schedule of events

Procedure	Visit 1a	Visit 1b	Visit 2 ⁴	Visit 3 ⁴	Visit 4	Visit 4a ⁴	Visit 4b ⁴	Visit 4c ⁴	Visit 5 -7	Visit 8 or EOS/ET	Visit 8a ⁴	Visit 8b ⁴	Visit 8c ⁴	Visit 8d ⁴	Visit 8e ⁴ EOS for optional Tx	
	Visits may be combined if subject meets eligibility criteria		72 hrs after Tx (±24 hrs)	14 days after Baseline (±3 days)	1 month ¹⁰ after Baseline (+7 days)	72 hrs after Optional touch-up (±24 hrs)	14 days after Optional touch-up (±3 days)	1 month ¹⁰ after Optional touch-up (+7 days)	3, 6, & 9 months ¹⁰ after Baseline (±7 days)	12 months ¹⁰ (±7 days) after Baseline	72 hrs after optional Tx (±24 hrs)	14 days after optional Tx (±3 days)	1 month after optional Tx (+7 days)	3 months ¹⁰ after optional Tx (±7 days)	6 months ¹⁰ after optional Tx (+7 days)	
	Screening Day -30 to 1	Baseline/ Tx Day 1	TC	Follow-up	Follow-up Optional TU	TC	Follow-up	Follow-up	Follow-up	Follow-up Optional Tx	TC	Follow-up	Follow-up	Follow-up	Follow-up	Follow-up
Informed Consent	X															
Med. Hx/prior therapies	X	X ^{1,2}														
Demographics	X															
Height/Weight ⁶		X ^{1,6}		X ⁶	X ⁶		X ⁶	X ⁶	X ⁶	X ⁶		X ⁶	X ⁶	X ⁶	X ⁶	
Inclusion/Exclusion Criteria	X	X ^{1,2}			X ^{1,5}					X ^{1,5}						
Urine pregnancy test ³	X	X ^{1,2}			X ^{1,5}					X ^{1,5}						
Vision Function Assessments	X	X ^{2,8,9}		X	X ^{5,8,9}		X			X ^{5,8}		X				
Randomization		X														
Treatment with study product		X ⁹			X ^{5,9}					X ⁵						
Evaluate device deficiencies		X			X ⁹					X ⁵						
Dispense Subject Diary		X ⁹			X ⁵					X ⁵						
Collect / Review Subject Diary			X ⁷	X	X ⁹	X ⁷	X	X			X ⁷	X	X			
2D Photography		X ¹		X	X ¹		X	X	X	X ¹		X	X	X	X	X
Concomitant Therapies	X	X ²	X	X	X	X	X	X	X	X	X	X	X	X	X	X

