8.1.1 Adverse Events of special interest

All incidences of visual disturbances, regardless of relationship to study product or seriousness, are considered Adverse Events of Special Interest (AESIs) and include but are not limited to the following: any change in vision, any loss of vision, blurry vision, double vision, pain in or around the eye, blind spot or shadow in the visual field, trouble moving eyes, any change in Snellen visual acuity including change of one line or greater.

AESIs should be reported (using the Adverse Event Clarification Form) within 24 hours of awareness to the Sponsor (following the instructions in section 8.5.6) via email to [contact]. Appropriate follow up should be conducted in order to determine the cause, severity, seriousness, outcome, and relationship to the study product or procedures.

8.2 **Vision function assessment**

Vision function assessments will be performed both prior to and 30 minutes post injection of the study product at baseline and optional touch-up and optional treatment. These assessments include Snellen visual acuity, extraocular muscle function, and confrontation visual field testing.

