8.2.1 Snellen visual acuity test

A Snellen Eye Chart will be used to assess visual acuity for distance vision. Visual Acuity will be conducted using the subject's best distance correction (e.g. contacts or eye glasses) at a distance of approximately 6 feet from the chart. Each eye will be measured separately by either using an occluder or having the subject cover each eye. The subject will be asked to start reading the letters at the top of the chart working their way to the bottom. The smallest row of letters that the subject can read will indicate their visual acuity listed on the chart. Snellen Visual Acuity will be recorded in their source documentation and eCRF. If there is one or more visual acuity line changes during the course of study, these should be reported to the Sponsor within 24 hours of awareness as an AESI. These events should be reviewed and assessed by the Investigator as an Adverse Event.

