#### Adverse Events of Special Interest (AESI)

2022-08-17 17:26

Due to the injection location of this study, AESIs will be considered and collected. All incidences of visual disturbances, regardless of relationship to study product or seriousness, will be considered as a potential AESI. These include, but are not limited to, the following: Any change in vision, any loss of vision, blurry vision, double vision, pain in or around the eye, blind spot or shadow in the visual field, trouble moving eyes, any change in Snellen visual acuity including change of one line or greater.

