#### 2.5.2 Adverse events

All AE data will be summarized by needle, cannula, and no treatment separately. Only AEs occurring after first injection, for subjects randomized to Restylane-L or after randomization for subjects randomized to No Treatment, or AEs that worsened, will be included in analysis. AEs occurring before, if any, will only be listed in subject data listings.

	Title 43USTT1904 Statistical analysis plan - Tear Trough	Doc id
GALDERMA		MA-42205

2022-08-17 17:26

All AE endpoints will be presented by the timepoint in which they occurred, defined as:

- No Treatment at Baseline: For subjects randomized to No Treatment, an AE which starts between date of randomization up until the time of their first injection.
- Initial Treatment with Restylane-L: For subjects randomized to Restylane-L, an AE which starts on or after their baseline injection up until their optional retreatment (including optional touch-up); for subjects randomized to No Treatment, an AE which starts on or after their optional initial treatment.
- Retreatment with Restylane-L: For subjects randomized to Restylane-L, an AE which starts on or after their optional retreatment.

Missing dates, severity, relationship, and seriousness will be imputed as described in Section 2.4.2. Adverse Events will be summarized by SOC and PT. The MedDRA version used for the coding will be noted as a footnote in the tables and listings.

A summary of AEs will be provided, which will include the number and percentage of subjects and number of events with the following categories of:

- Any AE
- Any Serious AE
- Any AE related to study product or injection procedure
- Any Serious AE related to study product or injection procedure
- Any AE unrelated to study product or injection procedure
- · Any Serious AE unrelated to study product or injection procedure
- Any AESI
- Any Serious AESI
- Number of subjects who did not have an AE

Summaries of related AEs (including the total number of events, number and percentage of subjects) will be displayed by treatment grouping specified above according to the following:

- All AEs related to study product or injection procedure by SOC, PT, and maximum intensity (mild, moderate, or severe)
- All AEs related to study product or injection procedure by SOC, PT, and duration of event
- All AEs related to study product or injection procedure by SOC, PT, and number of days to onset of event

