\*Visit is scheduled only if mitial treatment, optional touch-up or optional treatment is performed

Omitted if optional touch-up or optional treatment is not performed

Subject self-reported. Height only needs to be collected at baseline

Review diary with subject over the phone

Performed prior and 30 minutes post injection of study product

For subjects randomized to study treatment

One month is defined as 4 weeks in the study

ET = Early Termination

EOS = End of Study

GIHS = Galderma Infraorbital Hollows Scale

GAIS = Global Aesthetic Improvement Scale

TC= Telephone call

TU = Touch up

Tx = Treatment

Effective date: 2021-12-1713:25

Title 43USTT1904 Statistical analysis plan - Tear Trough

Doc id

Print date:

MA-42205

2022-08-17 17:26

CCI		

Doc id 43USTT1904 Statistical analysis plan - Tear Trough GALDERMA MA-42205

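### The any-AESI row counts one-line Snellen changes, but controls have no scheduled vision test between screening and Month 12, so its test-detected part is inflated in treated subjects

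*SAP*

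**What the plan says.** **What counts as an AESI.** Protocol 8.1.1 includes "any change in Snellen visual acuity including change of one line or greater", regardless of relationship or seriousness. Protocol 8.2.1 adds: "If there is one or more visual acuity line changes during the course of study, these should be reported to the Sponsor within 24 hours". It also asks the investigator to assess such changes as adverse events. The AESI paragraph of SAP 1.5.1 is slightly softer: "All incidences of visual disturbances, regardless of relationship to study product or seriousness, will be considered as a potential AESI".

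**When vision is tested.** Protocol 8.2 ties testing to injections, the last of them the one offered at Month 12: "Vision function assessments will be performed both prior to and 30 minutes post injection of the study product at baseline and optional touch-up and optional". In Protocol Table 1 (repeated in SAP Appendix G), the "Vision Function Assessments" row has:
- a screening test for everyone;
- Day 1 and Visit 4 tests limited by footnote 9 to subjects randomized to treatment;
- tests at Visits 3, 4b and 8b, which under footnote 4 take place only after the injection concerned;
- no test at Visits 5-7;
- a Visit 8 test under footnote 5: "Omitted if optional touch-up or optional treatment is not performed".

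**How AESIs are shown.** SAP 2.5.2 states: "All AE data will be summarized by needle, cannula, and no treatment separately". Its summary table has rows for any AESI and any serious AESI. The No Treatment period runs from randomization to the first injection, and percentages generally use the Safety population. SAP 2.5.4 has a separate table of Snellen worsening by eye, group and visit, whose denominator is subjects with a non-missing test at that visit.

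**The concern.** A one-line change can be found only if someone tests for it. The treated groups are tested repeatedly after baseline. Controls are not tested at all until Month 12, yet all of the approximately 47 stay in the AESI denominator and count as free of test-detected events. Letter-chart readings vary from one test to the next, so some one-line changes will appear in any group that is retested. The display would then show more AESIs after injection for a reason unrelated to injection.

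Visual disturbance is the only AESI category in this trial, so this row is the headline summary of the site-specific risk. As planned, it does not let a reader separate chance changes found by testing from a real effect or from complaints that subjects raise themselves.

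**Working it through.** The plan states no AESI rate and no safety precision figure, so there is nothing to reproduce beyond the arm sizes: 146 + 136 = 282 treated, and 282 + 47 = 329.

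**Step 1: count scheduled post-baseline tests before any Month 12 injection (Table 1 and footnotes).**

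| Subject | Tests | k |
|---|---|---|
| Treated, no touch-up | 30 min after injection; Visit 3 | 2 |
| Treated, with touch-up | the above; before and 30 min after touch-up; Visit 4b | 5 |
| Treated, retreated at Month 12 | one more, before that injection | 3 or 6 |
| Control, declines Month 12 treatment | none | 0 |
| Control, accepts Month 12 treatment | one, before that injection | 1 |

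The Visit 3 text in Protocol 4.7.4 has a parenthesis that could suggest controls attend. Footnote 4, and Protocol 4.7.2, which schedules Visit 3 for subjects randomized to treatment, settle that they do not.

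**Step 2: share flagged if injection has no effect.** Let q be the chance that one test shows a change of at least one line with no true change. The documents give no value, so q is **assumed** at 1%, 2%, 5% and 10%. With independent tests, the share flagged at least once is 1 − (1 − q)^k.

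| q | k = 2 | k = 5 | k = 6 | Control, k = 0 | Control, k = 1 |
|---|---|---|---|---|---|
| 1% | 2.0% | 4.9% | 5.9% | 0% | 1.0% |
| 2% | 4.0% | 9.6% | 11.4% | 0% | 2.0% |
| 5% | 9.8% | 22.6% | 26.5% | 0% | 5.0% |
| 10% | 19.0% | 41.0% | 46.9% | 0% | 10.0% |

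Example: q = 5%, k = 2 gives 1 − 0.95² = 9.75%. If no one had a touch-up, that is 0.0975 × 282 ≈ 27 treated subjects, against 0 of 47 controls before Month 12.

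**Step 3: relax independence.** Successive tests are compared with the same baseline reading, so their errors are positively related. The share flagged then lies between q (tests in full agreement) and 1 − (1 − q)^k (independent tests). For q = 5%, k = 2 it is 5.0% to 9.8%, or about 14 (0.05 × 282) to 27 of 282. The control figure before Month 12 stays at 0, so the direction does not change.

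**Step 4: the whole row.** Symptoms also count as AESIs. Assume, for illustration, an equal 2% symptom rate in both arms, independent of the tests. At q = 5% and k = 2, treated subjects show 1 − 0.98 × 0.95² = 11.6% and controls before Month 12 show 2.0%.

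**Step 5: what equal testing would give.** With subjects tested as denominator and the same k in each group, both show 1 − (1 − q)^k and the spurious difference is zero.

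**The case against.** The strongest reply has four parts.

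1. **Safety is descriptive only (Protocol 10.5).** No AESI difference is tested or estimated. This is true and limits the harm, but a percentage shown side by side can mislead without a p-value.
2. **SAP 2.5.4 already uses a tested denominator.** An untested control visit cannot appear there as a 0% rate, and every subject with a change in visual function is listed. This is real mitigation. But that table counts worsening only, whereas the AESI definition covers any change, and it leaves the AESI row in 2.5.2 as it is.
3. **AESIs include symptoms asked about in both arms.** This stands: only the test-detected part is certainly affected. Symptom capture is not equal either, because the 72-hour call, the day-14 visit and the 28-day diary belong to treated subjects.
4. **The rate and independence are assumptions.** This also stands. Dependence through a shared baseline reduces the figures, most of all for 5 or 6 tests.

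A reader might infer that a test-detected AESI is impossible in the No Treatment group, so that controls can give no background rate. The documents do not support this. The No Treatment period runs to the first injection, and controls who accept the Month 12 treatment are tested before it. A reader might also infer that testing distorts needle versus cannula. Both follow one schedule, so that contrast is affected only if touch-up or retreatment uptake differs. Finally, not every change found in treated subjects is an artefact; some may be real.

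**Conclusion.** The concern holds for treated versus no treatment, and for the test-detected part of the any-AESI row. With no effect of injection, that part is higher in treated subjects, because they have 2 to 6 scheduled post-baseline tests against 0 or 1 in controls. For any q above zero the direction before Month 12 is fixed by the schedule.

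The size is not known. At 1-10% per test with independent tests, about 2-19% of treated subjects with 2 tests would be flagged, against 0% of controls before Month 12; positive dependence lowers the treated figure towards q. Whether testing dominates the row as a whole cannot be settled from the documents, since neither the per-test rate nor the symptom rate is given. The primary endpoint is untouched. This is a cheap improvement to a descriptive safety table.

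**What to change.** In SAP 2.5.2, split the any-AESI row by source:

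- **(a) Symptom-reported events**, shown for all groups, with a footnote that treated subjects also have a 72-hour call, a day-14 visit and a 28-day diary.
- **(b) Changes found only on a scheduled vision test**, with subjects tested as denominator (the principle SAP 2.5.4 already uses) and with the numbers of subjects tested and of tests shown by group and period.

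For (b), mark controls as not tested before Month 12, but keep their Month 12 pre-injection test, expressed as change from screening, as never-injected reference data. The change from screening to the Day 1 pre-injection test, in treated subjects with separate visits, may be added as a second reference. It may be selected, because inclusion criterion 3 requires vision tests without findings and eligibility is re-confirmed on Day 1. The change from Visit 3 to the Visit 4 pre-injection test should not be called untreated: those subjects were injected on Day 1 and are the ones chosen for a touch-up.

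**Cost:** SAP wording, one derived flag and one extra table, with no added visit or test. The reference groups will be small and possibly selected, and the controls' Month 12 change spans a much longer interval than the early treated tests. AESI reporting to the sponsor is unchanged.

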4.1 General outline

This is a prospective, randomized, evaluator-blinded, no-treatment controlled, parallel group, multi-center US study to evaluate the effectiveness and safety of *Restylane-L* for correction of Infraorbital Hollows. Approximately 329 subjects will be included (CCI) to treatment (using needle or cannula) or to no treatment group. In the treatment group approximately 146 subjects will get injections using needle and approximately 136 subjects using cannula. Approximately 47 subjects will be randomized to no-treatment at baseline. The sites will be selected to use either needle or cannula for injection of all subjects randomized to treatment at their particular site. Approximately half of the sites will be using needle and the other using cannula for injection.

All randomized subjects' will have a GIHS score of 2 (Moderate) or 3 (Severe) with no more than one grade difference between the left and right side at baseline.

 <small>EST. 1981</small>	<small>Title</small> 43USTT1904 CSP Infraorbital Hollows	<small>Doc id</small> MA-40833
--	--	--

Effective date: 2021-12-15 20:29

Investigator blinding will be accomplished by using a Treating Investigator to administer the treatments and a Blinded Evaluator, to whom randomization and treatment are concealed, to conduct the blinded assessments. In addition, the Blinded Evaluator should not be allowed to retrieve study supplies or be present during the opening of the study supplies or injection procedure. All documents with information regarding study products and randomization assignment should be kept in a separate binder not available to the Blinded Evaluator. Safety assessments will be performed by non-blinded personnel.

Eligible subjects randomized to receive treatment will be injected by the Treating Investigator at Day 1. Optional touch-up treatment may be administered after 1 month of initial treatment, if deemed necessary by Treating Investigator and subject to obtain optimal aesthetic improvement. Optimal aesthetic improvement is defined as at least 1 grade improvement, from baseline, on the GIHS and best correction that can be achieved as agreed by the Treating Investigator and the subject. If optional touch-up is performed, a 72 hours telephone call, 14 day and 1 month follow-up visits should be scheduled.

Effectiveness and safety data will be collected for 12 months following the first injection.

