At the month 12 visit, the no-treatment comparator subjects will be offered an optional *Restylane-L* treatment. The subjects who received *Restylane-L* at the baseline visit will also be offered an optional additional treatment if optimal aesthetic improvement is not maintained (as determined by the Treating Investigator and subject). For subject receiving optional treatment at month 12 the effectiveness and safety data will be collected for another 6 months. A subject will be involved in the study for up to 19 months including 30 days screening and 6 months follow-up after optional treatment at month 12. The study visits are illustrated in Figure 1.

Effective

[figure not shown]
Version: 10.0

GALDERMA <small>EST. 1981</small>	Title 43USTT1904 CSP Infraorbital Hollows	Doc id MA-40833
---	---	---------------------------

Effective date: 2021-12-15 20:29

Effective

Version: 10.0

	Title 43USTT1904 CSP Infraorbital Hollows	Doc id MA-40833
--	---	---------------------------

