4.3 Duration of subject participation

The total duration of the study is approximately 19 months including 30 days screening period and 6 months follow-up after optional treatment at month 12. One month is defined as 4 weeks in the study.

End of study is when enrolment has reached the target number of subjects and all subjects have completed the last study visit.

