- Interview subject regarding any AEs that have occurred since receiving treatment. If AEs are reported, notify the Investigator immediately and determine whether subject should return to the site for an unscheduled visit. The Investigator should assess all reported AEs in a timely manner.
- Interview subject regarding the Diary completion and reported events since receiving treatment. Remind subject to complete the Diary daily and bring it to the next on-site visit.
- Remind the subject of the next on-site visit.

4.7.12 Visit 8b: Follow up visit 14 days (\pm 3 days) after optional touch-up performed

This visit should only be conducted for subjects who received a treatment at Visit 8.

- Interview subject regarding any concomitant therapies and record subject's weight.
- Interview subject and evaluate any AEs, and post-treatment AEs by Treating Investigator (if randomized to treatment) that have occurred since the last visit.
- Obtain photographs.
- Perform Vision Function Assessments.
- Interview subject regarding the Diary completion and reported events since receiving treatment. Remind subject to complete the Diary daily and bring it to the next on-site visit.
- Remind subject of the next scheduled on-site visit.

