### 1.1 Background

#### 1.1.1 Study design

This is a prospective, randomized, evaluator-blinded, no-treatment controlled, parallel group, multicenter US study to evaluate the effectiveness and safety of Restylane-L for correction of Infraorbital Hollows (IOH). Eligible subjects randomized to receive treatment will be injected by the Treating Investigator at Day 1. Optional touch-up treatment may be administered after 1 month of initial treatment, if deemed necessary by Treating Investigator and subject to obtain optimal aesthetic improvement. Optimal aesthetic improvement is defined as at least 1 grade improvement, from baseline, on the GIHS and best correction that can be achieved as agreed by the Treating Investigator and the subject.

At the month 12 visit, the no-treatment comparator subjects will be offered an optional Restylane-L treatment. The subjects who received Restylane-L at the baseline visit will also be offered an optional additional treatment if optimal aesthetic improvement is not maintained (as determined by the Treating Investigator and subject). For subjects receiving optional treatment at month 12 the effectiveness and safety data will be collected for another 6 months. A subject will be involved in the study for up to 19 months including 30 days screening and 6 months follow-up after optional treatment at month 12. The study flow chart is provided in Appendix A.

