#### Injection Volume Administered

The injection volume (mL) administered throughout the study will be presented descriptively by the following timepoints, by group (where applicable):

- Initial treatment The amount of study product injected into subjects at the baseline visit (for subjects randomized to Restylane-L) or at the Month 12 visit (for subjects randomized to No Treatment).
- Optional Touch-up The amount of study product injected into subjects at the Month 1 visit. Only applicable to subjects randomized to Restylane-L.
- Initial treatment + Touch-up The cumulative sum of study product injected into subjects for the initial and touch-up treatments, regardless of how many treatments a subject received. This will be presented for both treatment groups.
- Re-Treatment The amount of study product injected into subjects at the Month 12 visit.
   Only applicable to subjects randomized to Restylane-L.
- Total injected volume The cumulative sum of study product injected into subjects across
  every potential injection timepoint, regardless of how many injections a subject got. This
  will be presented for both treatment groups.

If a subject receives more than one injection for a given treatment period, their total volume from all injections will be summarized in the 'Total injected volume' timepoint. Only the injection given closest to the protocol-specified injection visit (Appendix G) will be presented in each respective timepoint section described above.

All injection volume, injection characteristics, procedural anesthetics, and injection concomitant procedures data will be presented by treatment and subject in data listings.

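### The Initial Treatment and Retreatment adverse-event percentages cover unequal windows and numbers of sessions, with no common-window table and no stated period denominator

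*SAP*

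**What the plan says.** SAP 2.5.2 presents every AE endpoint by period. For the Restylane-L arm, Initial Treatment runs from the baseline injection "up until their optional retreatment (including optional touch-up"). For the control arm it is "for subjects randomized to No Treatment, an AE which starts on or after their optional initial treatment". Retreatment contains the Restylane-L arm only, from the optional Month 12 injection onward.

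The lengths come from Protocol 4.1 and 4.3: "Effectiveness and safety data will be collected for 12 months following the first injection"; for those "receiving optional treatment at month 12 the effectiveness and safety data will be collected for another 6 months"; and "One month is defined as 4 weeks in the study". SAP 2.5.1 defines the touch-up volume as "The amount of study product injected into subjects at the Month 1 visit" and confines it to the Restylane-L arm.

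The planned summaries are numbers of subjects, percentages and numbers of events. The visible text has no common window and no exposure-adjusted rate. The denominator is, in general, the Safety population. AE data are to be split by needle, cannula and no treatment (SAP 2.5.2), with the Safety population analysed as treated (SAP 2.2). Neither section says which column holds a control's AEs after the Month 12 injection.

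Protocol 4.7.12 (Visit 8b) has staff evaluate any AEs and also "post-treatment AEs by Treating Investigator (if randomized to treatment) that have occurred since the last visit". Protocol 4.7.13 (Visit 8c) asks for the Treating Investigator's post-treatment evaluation without that parenthesis.

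**The concern.** A reader who sees the two periods side by side will read the percentages as the risk of first treatment and of repeat treatment. They measure different things: up to 48 weeks with one or two sessions against 24 weeks with one. Retreatment can look safer because less time and fewer sessions are counted, or because many people who were never retreated sit in the denominator. Safety is a stated purpose of the study, and the data are meant to support a US marketing application (Protocol 2.3), so these percentages will be relied on.

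The Initial Treatment period also mixes two exposures, and the column for injected controls is left open. At Visit 8b, every attendee has been injected at Visit 8, yet one of the AE evaluations is worded to leave out subjects randomized to no treatment.

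**Working it through.** **Inputs from the documents.** One month is 4 weeks (Protocol 4.3). Follow-up is 12 months after first injection and 6 months after the optional treatment (Protocol 4.1). About 282 subjects are randomized to Restylane-L and 47 to no treatment (Protocol 10.11, SAP 2.7).

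**Assumed, because no figures are given.** AE risk per subject 5–60% over 48 weeks, or 5–40% per session; touch-up share 0–100%; control uptake at Month 12 50–100%; share of the 282 retreated 30–70%.

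**Reproducing the plan's figures.** Screening of about 1 month + 12 + 6 = 19 months, as stated. 282 + 47 = 329, as stated. Windows: 12 × 4 = 48 weeks and 6 × 4 = 24 weeks.

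**Share of controls in the Initial Treatment period.** At full uptake: 47/329 = 14.3% of subjects. Person-weeks: 47 × 24 = 1,128 of 282 × 48 + 1,128 = 14,664, or 7.7%. Mean follow-up falls from 48 to 14,664/329 = 44.6 weeks. At 50% uptake the shares are 7.7% of subjects and 4.0% of person-weeks.

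**Model A: constant hazard, the same in every period.** If the 48-week risk is pA, the 24-week risk is pB = 1 − (1 − pA)^(24/48). With controls pooled at full uptake, the Initial Treatment risk is m = (282·pA + 47·pB)/329. Example with pA = 10%: pB = 1 − 0.9^0.5 = 5.13%; m = (282 × 10 + 47 × 5.13)/329 = 9.30%.

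| pA | pB (= Retreatment) | m | relative loss 1 − m/pA | pA/pB | m/pB |
|---|---|---|---|---|---|
| 5% | 2.53% | 4.65% | 7.05% | 1.98 | 1.84 |
| 10% | 5.13% | 9.30% | 6.95% | 1.95 | 1.81 |
| 20% | 10.56% | 18.65% | 6.74% | 1.89 | 1.77 |
| 40% | 22.54% | 37.51% | 6.24% | 1.78 | 1.66 |
| 60% | 36.75% | 56.68% | 5.53% | 1.63 | 1.54 |

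At 50% uptake the relative loss is 3.0–3.8%.

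**Model B: risk q per session, no late events, touch-up share u.** Here pA = 1 − (1 − q)(1 − uq) and pB = q. For q = 10%:

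| u | pA | m | relative loss | pA/pB | m/pB |
|---|---|---|---|---|---|
| 0% | 10.0% | 10.0% | 0% | 1.00 | 1.00 |
| 50% | 14.5% | 13.9% | 4.4% | 1.45 | 1.39 |
| 100% | 19.0% | 17.7% | 6.8% | 1.90 | 1.77 |

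Over q = 5–40% the relative loss is 0–7.0%.

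**Direction.** In both models, wherever the periods differ, taking the controls out moves the Initial/Retreatment ratio further from 1 (1.81 to 1.95 at pA = 10%). The gap therefore comes from the Restylane-L arm, not from the controls.

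**Denominator.** Suppose the true Retreatment risk is 10% among those retreated and 30–70% of 282 are retreated. Divided by 329: 0.10 × 84.6/329 = 2.6% up to 0.10 × 197.4/329 = 6.0%, a relative loss of 74% down to 40%. Divided by 282, the display is 3.0–7.0%.

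**The case against.** The plan makes no formal comparison of the two periods, and Protocol 10.5 calls the safety analysis descriptive. Onset is counted from the most recent treatment, AEs starting more than 21 days after it are listed, by-subject listings give onset and duration, and the diary covers an equal 28 days after each treatment. Protocol 2.4 says common reactions generally resolve in one to two weeks and most AEs arise within days to weeks, a span that injected controls also complete. All of this stands and limits the harm. It does not put the tabulated percentages on a common footing: the same section also reports swelling and serious infection weeks to months later, and touch-up gives the first period a second session even for early events.

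Four stronger readings are tempting, and the documents do not support them.

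- That mixing in the controls causes the non-comparability. It slightly narrows the gap.
- That the controls heavily dilute the rates, for example 10% falling to 10% × 282/329 = 8.6%. That is the ceiling, for events that controls cannot contribute at all, such as those after week 24 or after touch-up. No rate for such events is given. Pooling is likely under the as-treated rule but not explicit; if controls keep a No Treatment column, the needle and cannula columns are not diluted.
- That retreatment would look about half as risky. This needs a constant hazard over 48 weeks, which Protocol 2.4 contradicts for injection reactions, or touch-up in nearly everyone.
- That controls' AEs go unrecorded at Visit 8b. The general AE evaluation there covers every attendee, and Visit 8c has no restriction. The wording looks carried over from Visit 4b, where it does no harm.

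**Conclusion.** The point holds as one of presentation and definition. The two periods' crude percentages should not be read against each other. With no true difference in risk, the ratio is 1.54–1.98 under a constant hazard and 1.00–1.95 under a per-session model, with or without controls. The cause is the Restylane-L arm's 48 against 24 weeks and its possible second session.

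The contribution of delayed-treatment controls is modest: at most 14.3% of subjects at full uptake, with relative dilution of about 7% or less in the models tried, and none if they are not pooled. Both models assume that controls carry the same hazard or session risk as everyone else; the documents neither show nor deny this. The denominator rule matters more if it is applied literally to Retreatment, but its general wording leaves room for exceptions. Uptake, touch-up share, retreatment share and AE risks are all assumptions.

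The Visit 8b wording is a small internal inconsistency, not evidence of lost AE data.

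**What to change.** In SAP 2.5.2:

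1. Add a descriptive AE table for a common window, the first 24 weeks after the first injection of each period, with and without subjects who had a touch-up. The touch-up split is descriptive only, since who receives one is not random.
2. State that the denominator for each period is the number of subjects injected in that period.
3. Show delayed-treatment controls as their own column within Initial Treatment, which also settles where their AEs go.

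Keep the full-period table: AEs after week 24 in the Restylane-L arm would appear only there. Splitting out the controls without the common-window table would not help, because it slightly widens the gap between the periods.

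In the protocol, reconcile 4.7.12 (Visit 8b) with 4.7.13 (Visit 8c) and with the fact that all Visit 8b attendees, controls included, were injected at Visit 8.

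The cost is one table, one column, a sentence on denominators and one wording correction. No new data are needed for the tables.
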